In addition to the above-mentioned recruitment sources, we will also be able to recruit from the Community Health Care Van (CHCV). The CHCV, a 36-foot van is equipped with two exam rooms, a counseling/phlebotomy room and a waiting area. Partial support from NIDA (R01-DA10186) has enabled the CHCV project to expand service delivery and to reach a number of goals which improve the health care of out-of-treatment drug users. The program currently operates five days (and some evenings) a week in five underserved neighborhoods in New Haven. The CHCV is staffed by a full-time clinical coordinator, a drug treatment coordinator, a case

[figure not shown]
manager, HIV counselors, social workers, mental health workers, clinicians from several hospitals and community health care centers and a dedicated driver/outreach worker. The staff has developed strategic liaisons with patients and providers throughout the community and is capable of connecting researchers with potential HIV-infected patients with co-occurring substance abuse issues.

[figure not shown]
[figure not shown]
[figure not shown]
For the fourth arm, we will be asking the participants to provide us with three names of people in their social network, who has a phone and are willing to send them weekly text reminder to take their medication. Out of the three people, one person will be chosen by the RA to be the social designee. The RA will be contacting all three social designees via phone and upon verbal consent, the social designee will be provided information about the study and their role, and reminded to send text messages to the participants on the weekly basis.

4. Screening Procedures

- a. Will email or telephone correspondence be used to screen potential subjects for eligibility prior to the potential subject coming to the research office? Yes No
- b. If yes, identify below all health information to be collected as part of screening and check off any of the following HIPAA identifiers to be collected and retained by the research team during this screening process.

HEALTH INFORMATION TO BE COLLECTED:

9. **Process of Consent/Assent:** Describe the setting and conditions under which consent/assent will be obtained, including parental permission or surrogate permission and the steps taken to ensure subjects' independent decision-making.

Aim 1 (Focus Groups): Yale IRB-approved fliers will be used to help with recruitment for FGs with cocaine-using individuals and the drug treatment counselors will also assist in recruitment of participants. For the FGs with healthcare providers, IRB-approved flyers containing a toll-free number will be posted in the offices of all five HIV clinics in the Ryan White Consortium. When recruiting participants from venues, the participants will be briefly told about the FG and if they want to learn more about it, recruiters will hand out a contact information card to call into the study site. No information will be collected from them at this time so they may choose to not to call into the site or if they do call in and want to come in for consenting, information is still not collected and they may decline to come in. During the consent process, they will be read the consent form verbatim and will be asked if they would like to participate in the study or not. They will also be able to decline or take more time to think about it. If they verbally consent, another appointment will be scheduled for the participant to come in and participate in the focus group.

Aim 2 (Pilot Feasibility Study): Yale IRB-approved fliers will be used to help with recruitment for the RCT and the drug treatment counselors will also assist in recruitment of participants. When recruiting participants from venues, participants will be briefly told about the study and if they want to learn more about it, recruiters will hand out a contact information card to call into the study site. No information will be collected from them at this time so they may choose to not to call into the site or if they do call in and want to come in for consenting, information is still not collected and they may decline to come in. Participants will be provided an informed consent form that will be approved through the Yale University School of Medicine Institutional Review Board (IRB). The participant will be read the consent form verbatim and will be asked if they would like to participate in the study or not. The consent form will outline the agreement to participate in this research study. Participants will indicate consent by signing and dating the informed consent form. All patients will be reminded that their refusal to participate will not negatively affect their relationship with Yale University, local SAT or hospital facilities, their ability to continue in drug treatment, or their ability to obtain medical services from area clinics in the future. They will also be able to decline or take more time to think about it. If they agree, they will be asked to sign the consent form. They may choose to withdraw from the study at any point.

In addition, the following process of consent is going to be followed for the designated social network member for the fourth arm intervention (TRIDENT): a) after randomized to the 4th arm, the RAs and/or the Project Coordinator will ask the participant to call his/her designated social network member, b) the participant will explain the study details from an information sheet to the designee. At this stage the RAs and/or the Project Coordinator will also help in explaining the role

of the designee in the intervention, c) We will obtain a verbal consent from the designees as minimal risk is involved. The risk is minimal for designees because: a) the designees are not answering any questions, b) they are not completing any surveys at the study sites, c) they will use their own phone to send text messages to the participant, d) the data from the messages will be downloaded from the patient's phone and not from the designee's phone, and e) after obtaining the verbal consent, the designee will be given a unique ID and their name or phone number will not be used.

10. Evaluation of Subject(s) Capacity to Provide Informed Consent/Assent: Indicate how the personnel obtaining consent will assess the potential subject's ability and capacity to consent to the research being proposed.

The study interviewers are trained in interviewing and will assess the subject's understanding through verbal responses and non-verbal cues. Interviewers will ask open ended questions while introducing the details of the study to the subject such as "Can you tell me what you understood from our discussion?" or "What should you do if you want to stop participating in this study?" and will use IRB approved consent forms during informed consent procedure. If the interviewer determines that the subject does not fully comprehend the study purpose and his or her role as a participant, the subject will not be consented and will not be eligible for the study.

11. Documentation of Consent/Assent: Specify the documents that will be used during the consent/assent process. Copies of all documents should be appended to the protocol, in the same format that they will be given to subjects.

Aim 1 (Focus Groups): No signed consent forms will be required for the focus group participants since signatures would be the only identifiers. An IRB-approved consent form will be read verbatim and assent will be given verbally. Additionally, a copy of the consent form will be given to the participants.

Aim 2 (Pilot Feasibility Study): A compound consent and authorization form will be used (attached in this application).

No signed consent forms will be required for the designated social network members, involved in the 4th arm of Aim 2, since their health and personal identifiers are not used in the study. An IRB-approved information sheet will be read verbatim and assent will be given verbally. A unique ID will be provided for the designee and their names will not be used.

12. Non-English Speaking Subjects: Explain provisions in place to ensure comprehension for research involving non-English speaking subjects. If enrollment of these subjects is anticipated, translated copies of all consent materials must be submitted for approval prior to use.

All consent forms, information sheets and study documents will be available in English and Spanish. Our team consists of individuals who are bi-lingual/bi-cultural in Spanish and English.

[figure not shown]
12(a) As a limited alternative to the above requirement, will you use the short form* for consenting process if you unexpectedly encounter a non-English speaking individual interested in study participation and the translation of the long form is not possible prior to intended enrollment?

YES NO

Note* If more than 2 study participants are enrolled using a short form translated into the same language, then the full consent form should be translated into that language for use the next time a subject speaking that language is to be enrolled.

Several translated short form templates are found on our website at: <http://www.yale.edu/hrpp/forms-templates/biomedical.html>. If the translation of the short form is not available on our website, then the translated short form needs to be submitted to the IRB office for approval via amendment prior to enrolling the subject. *Please review the guidance and presentation on use of the short form available on the HRPP website.*

If using a short form without a translated HIPAA Research Authorization Form, please request a HIPAA waiver in the section above.

SECTION VIII: PROTECTION OF RESEARCH SUBJECTS

Confidentiality & Security of Data:

- a. What protected health information (medical information along with the HIPAA identifiers) about subjects will be collected and used for the research?

Private identifiable data about study participants including their names, age, sex, ethnicity, addresses, phone numbers and other contact information, photos, dates of birth will be collected. Names and phone numbers will be collected from social designee for the fourth arm. All confidential information (study instruments etc.) will be recorded with study participant number only, maintained in locked cabinets within our offices at the Yale University AIDS Program and will only be available to be opened by the Data Manager, Project Manager or the Principal Investigator.

- b. How will the research data be collected, recorded and stored?

Aim 1 (Focus Groups): FG guides will be prepared that detail the conduct during and after the interview, including not using names, not discussing specific illegal activities, and maintaining the confidentiality of focus group participants. Materials will consist of interviews with the participants that have been described previously that will be audio-recorded and then transcribed. The audio files from all of the FGs will be sent to a licensed professional transcription service using secure and encrypted transfer systems.

Aim 2 (Pilot Feasibility Study): The research materials of interest in this study include structured questionnaire data (primarily using standardized and validated measures), laboratory data obtained at Quest Diagnostics laboratories, chart review, and biological measures obtained at research sites including urinary toxicology screens, data obtained through participants sending pictures of blister packs, and survey data obtained through the smartphone app-based survey. All such materials and questionnaire data (excluding laboratory data) will be specifically obtained for research purposes.

Data Sources:

1. *Structured Interviews:* Structured interviews will include: (1) demographics; (2) health status, including past medical history and current medications; (3) depressive symptoms using the CES-D;¹³⁶ (4) standardized measures of drug use, including determination of DSM-V criteria¹²² for severity of cocaine use; (5) Addiction Severity Index (ASI)-Lite to assess cocaine use, polysubstance use and severity on HIV outcomes;¹³⁷ (6) ART adherence using the Smart Pill Box, Visual Analog Scale (VAS) and brief adherence scale;^{126,127} (8) change in cocaine use using the Timeline Follow-Back (TLFB);¹²⁸ (9) AUDIT-C to assess alcohol use;¹²⁹ (10) health literacy;¹³⁰ (11) social support;¹³¹ (12) trust in physicians;¹³² (13) acceptance of smartphones;¹³³ and (14) perceived source credibility¹³⁴, (15) neighborhood effects using the Activity Space questionnaire, and (16) egocentric social network inventory to understand support and risk networks.

2. Photos of blister pack: We will be asking participants to text the image of the medication blister pack every week. This method will be used to count the pills they have taken in the week, and hence, adherence will be determined using this source.

3. *Smart phone app survey*: During the intervention period, a smartphone app built on the open-source CommCare platform (powered by Dimagi, Inc.) will be used to collect weekly data from participants. The weekly survey data will be stored on HIPAA-compliant CommCare servers and transferred to Yale-secured and encrypted computers periodically. As per Yale HIPAA Privacy rules, Business Associates Agreements (BAA) will be established between vendors such as Dimagi, Inc., which will store the Protected Health Information (PHI) of the participants.

4. *Laboratory Measurements*: We have a prearranged system for phlebotomy, reporting of results and storing of specimens at -70C through Quest Diagnostics. Because tests are not experiment, all results (HIV VL, CD4 and genotypic analyses) will be sent to the participants' providers, including HIV-1 RNA testing (Amplicor 1.5, range 20 to 750,000 copies/mL) and CD4 lymphocyte count at baseline, and end of intervention (12 weeks) . HIV genotypic mutations will be assessed at baseline and at 16 weeks (if VL>500 copies/mL).

33

5. *Chart Review*: During consenting procedures, a medical release of information (ROI) will be obtained to allow research staff to review medical records at drug and alcohol treatment, local hospitals, pharmacies and HIV care sites. Medical records will be retrieved to confirm self-reports of healthcare utilization, HIV status, documented medical history and prescribed medications. The ROI will allow us to communicate with medical, psychiatric and drug treatment providers to inform them that their patient will be in an adherence study, to alert research staff of any changes in ART medication, and in case of the participant becoming acutely ill.

6. Text messages/SMS download: A total of 4 text messages (one text message per week) sent by the designated social network member to the participant will be downloaded. The text messages will be downloaded by a RA from the participant's cell phone after receiving consent from the participants All phones are will be password protected and encrypted.

Storage of Data: All information will be stored in password-protected computers with double-password protection for opening specified files. The computers in our research facility have been encrypted in accordance to HIPAA guidelines. NetIDs of all research personnel will be provided to the IRB and to the IT Services for verification for encryption. If new members are added to the research team, and if personal computers were to be used for accessing PHI, all such machines will need to be Yale encrypted and verified by the IT service office. For the duration of the pilot study, medication adherence data obtained through the use of smart pill boxes will be stored in a secure, encrypted cloud system owned by TowerView Health® Corp. This data will be erased once it has been transferred securely to our research computers. Similarly, CommCare survey data will be saved on a central server owned by Dimagi, Inc. until it has been securely transferred to our computers. In addition, data collected from the Activity Space, and Social Network Questionnaire will be saved on Microsoft's cloud computing platform called University of Connecticut's (UConn) instance of Microsoft Azure, which is also compliant with UConn's and similar to Yale's HIPAA policy. UConn's UITS offers the use of a HIPAA approved

instance of Microsoft Azure as a service. A BAA from UConn will be provided to Yale IRB. We are using UConn's Azure service for the following reasons:

- [name], a Co-PI/collaborator of this study, and her team from UConn have built an android based survey app using PowerApps, which is connected to UConn's Azure platform.
- The data that will be collected using this survey will be stored on UConn's Azure SQL database
- Only [name] has access to that database and uses her UConn's administrator netID to login.

. Text download/ SMS from participants (fourth arm) will initially be stored in a secure Yale Dropbox which will protected by unique password available only to the project staff. All research data will be stored in the double-locked research offices within the Clinical and Community Research Program within the Yale University AIDS Program. Client level data will be stored with the research study number and without any unique identifiers. All identifiers that link study number to study subject will be housed in PGP encrypted, password-protected computers available only to the Data Manager/Statistician, Project Director and the Principal Investigator. All computers used for study purposes have been PGP encrypted to meet all HIPAA requirements. During the 20 years of [name] research experience, there has never been a breach in confidential data. The data will be stored in the manner noted above for at least seven years after completion of the study. All confidential information (study instruments, pharmacy record, etc.) will be recorded with the study participant number only and maintained in locked cabinets within our offices at the Yale University AIDS Program and will only be available to be opened by the Data Manager, Project Director or the Principal Investigator. These data will be analyzed so that the findings can contribute to scientific literature that could be used to develop effective interventions for HIV+ cocaine users. All files will be stored in locked cabinets in a locked facility.

- c. How will the digital data be stored? CD DVD Flash Drive Portable Hard Drive Secured Server Laptop Computer Desktop Computer Other
- d. What methods and procedures will be used to safeguard the confidentiality and security of the identifiable study data and the storage media indicated above during and after the subject's participation in the study?

All information will be stored in password-protected computers with double-password protection for opening specified files. The computers in our research facility have been encrypted in accordance to HIPAA guidelines. For new personnel added to the team or use of personal computers will be encrypted by the ITS. For the duration of the pilot study, medication adherence data obtained through the use of smart pill boxes will be stored in a secure, encrypted cloud system owned by TowerView Health® Corp. This data will be erased once it has been transferred securely to our research computers. Similarly, the smart phone app survey data will be saved on a central server owned by HIPAA-compliant CommCare and UConn Microsoft Azure Cloud until it has been securely transferred to our computers. All research data will be stored in the double-locked research offices within the Clinical and Community Research Program within the Yale University AIDS Program. Client level data will be stored with the research study number and without any unique identifiers. All identifiers that link study number to study subject will be housed in PGP encrypted, password-

protected computers available only to the Data Manager/Statistician, Project Director and the Principal Investigator.

Do all portable devices contain encryption software? Yes No

If no, see <http://hipaa.yale.edu/guidance/policy.html>

- e. What will be done with the data when the research is completed? Are there plans to destroy the identifiable data? If yes, describe how, by whom and when identifiers will be destroyed. If no, describe how the data and/or identifiers will be secured.

The data will be stored in the manner noted above for at least seven years after completion of the study. All confidential information (study instruments, pharmacy record, etc.) , collected in paper format, will be recorded with the study participant number only and maintained in locked cabinets within our offices at the Yale University AIDS Program and will only be available to be opened by the Data Manager, Project Director or the Principal Investigator. Data collected from online platforms such as CommCare and saved in soft copy format will be stored in the Yale shared folder (J drive). Only the Data Manager, Project Director, the PI, and Co-Is, with valid Yale NetIDs and special permission from the Yale administrator, will have access to this data. With the guidance of the Yale University Information Technology Services and HIPAA departments, data will be destroyed to ensure proper methodology is used when shredding files and deleting computer files. In addition, all the text messages will be "shredded" using PGP Desktop Shred which removes all traces of the file on the computer.

- f. Who will have access to the protected health information (such as the research sponsor, the investigator, the research staff, all research monitors, FDA, Yale Cancer Center Data and Safety Monitoring Committee (DSMC), SSC, etc.)? (please distinguish between PHI and de-identified data)

The Principal Investigator, Co-Investigator, and research staff will have access to the data.

[figure not shown]
[figure not shown]
[name], Assistant Professor in the Department of Communication at the University of Missouri Columbia, will also have access to the data. University of Missouri, Columbia is a site that will be relying on Yale IRB review for the limited engagement of [name] for obtaining identifiable data.

- g. If appropriate, has a [Certificate of Confidentiality](#) been obtained?

Yes, the Certificate of Confidentiality from National Institute on Drug Abuse (NIDA) has been obtained on May 22, 2017.

- h. Are any of the study procedures likely to yield information subject to mandatory reporting requirements? (e.g. HIV testing – reporting of communicable diseases; parent interview -incidents of child abuse, elderly abuse, etc.). Please verify to whom such instances will need to be reported.

Attempts to harm oneself or someone else will be reported to the proper authorities.

References:

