[Redacted text line]

[Redacted text line]

[Redacted text block]

1. **Statement of Purpose:** State the scientific aim(s) of the study, or the hypotheses to be tested.

The aim of this study is to examine the effect of mHealth tools on antiretroviral (ART) adherence and persistence among HIV-infected individuals with co-occurring cocaine use disorders (CUDs). The specific aims are:

- (1) To conduct qualitative assessments using focus groups of people living with HIV (PLH) who use cocaine and healthcare providers that will assess the acceptability, feasibility, facilitators and barriers of implementing mHealth interventions; and will aid in developing the final design and content of both automated and clinician feedback in preparation for designing a pilot feasibility study.
- (2) To conduct a 12-week pilot feasibility RCT among PLH with co-occurring CUDs that will examine the impact of mHealth tools (cellular-enabled smart pill boxes and cell phones) and feedback (no feedback vs. automated feedback vs. automated + clinician feedback vs. vs. automated + text-reminder from a social network) on primary (ART adherence and persistence) and secondary outcomes (HIV viral suppression, cocaine use, retention in HIV care).

The hypotheses include:

- (1) Patients with automated feedback + clinician feedback will have higher ART adherence and persistence than patients with only automated feedback and patients with no feedback.
- (2) Patients with automated feedback + clinician feedback will have improved HIV outcomes including lower changes in log₁₀ HIV-1 RNA levels, higher CD4 counts and higher rates of retention in care, compared to patients with only automated feedback and patients with no feedback.
- (3) Patients with automated feedback + clinician feedback will have decreased cocaine use compared to patients with only automated feedback and patients with no feedback.
- (4) Patients with automated feedback + text-reminder from a social network will have higher ART adherence and persistence than patients with only automated feedback and patients with no feedback.
- (5) Patients with automated feedback + text-reminder from a social network will have improved HIV outcomes including lower changes in log₁₀ HIV-1 RNA levels, higher CD4 counts and higher rates of retention in care, compared to patients with only automated feedback and patients with no feedback.

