After the 12-week intervention, all participants will be followed for a 4-week period and primary and secondary outcomes will also be recorded during the post-intervention follow-up period.

3. Monthly Research Interviews: Monthly interviews will take place for the 16-week duration of the study (12-week intervention and 4-week follow-up) for all participants. The interviews will include health care utilization, phlebotomy, self-reports of drug use, and mental illness. All phlebotomy information obtained after community release will be obtained through Quest Diagnostics, a national reference laboratory. We have a prearranged system for phlebotomy, reporting of results and storing specimens at -70C that has been in place for the past decade. None of the assays used are experimental and will be drawn as part of clinical care at standardized times as outlined. Tests will include HIV-1 RNA testing (Amplicor 1.5, range 50 to 750,000 copies/mL) and CD4 lymphocyte count using flow cytometry at baseline, end of intervention (12 weeks) and end of follow-up period (16 weeks). HIV genotypic mutations will be assessed at baseline and at 16 weeks (if VL>500 copies/mL).

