Aim 2 (Pilot Feasibility Study): The primary outcomes will be ART adherence and persistence, measured as a composite score ranging from 0 to 100%, and as number of continuous days taking ART without a 7-day (or 3-day) gap^{18,71} respectively. Outcome analyses will be conducted for (a) adherence and persistence behavior, (b) drug outcomes (cocaine use), (c) HIV treatment outcomes (VL<20 copies/mL; change in CD4+ T lymphocytes), and (d) ART-related Information, Motivation, and Behavioral Skills constructs. The general framework for discerning differences between study conditions on main outcome variables will be to perform 3 (intervention condition) x 3 (repeated follow-up assessments) mixed design analysis entering pre-intervention scores as covariates and additional theoretically and empirically relevant covariates (such as baseline mental status etc.). For variables that are approximately normally distributed, we will use multivariate analyses of covariance (MANCOVA), with significant multivariate tests followed by subsequent analyses of co-variance (ANCOVA). Variables that violate distributional assumptions of normality will be analyzed using generalized linear model (GLM) procedures, which enable the use of non-Gaussian error models. Based on a review of the literature, GLM is the most appropriate approach for variables with strong positive skew, e.g., adherence.

[figure not shown]
To examine the mediating and moderating effects of activity space and social network facilitators and barriers on primary (ART adherence and persistence) and secondary outcomes (HIV viral suppression, cocaine use, retention in HIV care), the following steps are going to be followed:

- a. A range of variables associated to activity space and social networks (both risk and support) will be calculated using a combination of GIS, SNA, and spatial statistics methods. The variables will be the covariates.
- b. The outcome variables are: primary (ART adherence and persistence) and secondary outcomes (HIV viral suppression, cocaine use, retention in HIV care).
- c. We will first use descriptive statistics, bivariate correlation, and t-tests to understand the distribution and association of all the covariates calculated in step#a with the outcome variables (step#b).
- d. After running tests of multicollinearity, only uncorrelated covariates at $p \leq 0.05$ (considered statistically significant) will be included in the subsequent mediation and moderation analysis.

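### The log10 HIV-1 RNA element of hypotheses 2 and 5 has no defined sign and no matching analysis, because viral load is analysed only as VL<20 copies/mL

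*Combined protocol and SAP*

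**What the plan says.** **Hypotheses.** In Section 1 (Statement of Purpose), hypotheses 2 (clinician feedback) and 5 (social-network text reminder) each say that patients "will have improved HIV outcomes including lower changes in" log10 HIV-1 RNA levels, followed by "higher CD4 counts and higher rates of retention in care, compared to patients with only automated feedback and patients with no feedback". Each hypothesis thus has three elements: RNA, CD4 and retention.

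**Declared outcome.** Aim 2 in the same section lists "secondary outcomes (HIV viral suppression, cocaine use, retention in HIV care". At this level viral load is a suppression outcome, not a change.

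**Analysis.** Section 12 (Statistical Considerations, Aim 2) gives "HIV treatment outcomes (VL<20 copies/mL; change in CD4+ T lymphocytes" among its outcome groups. The general model is a "3 (intervention condition) x 3 (repeated follow-up assessments) mixed design analysis entering pre-intervention scores as covariates". The mediation and moderation step in the same section says: "The outcome variables are: primary (ART adherence and persistence) and secondary outcomes (HIV viral suppression, cocaine use, retention in HIV care".

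**Measurement.** Research Plan 2.E, item 3 (Monthly Research Interviews) specifies "HIV-1 RNA testing (Amplicor 1.5, range 50 to 750,000 copies/mL", drawn at baseline, week 12 and week 16. Section VIII, Data Sources, item 4 (Laboratory Measurements) gives a range of 20 to 750,000 copies/mL for the same assay, at baseline and week 12 only.

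**The concern.** The hypotheses make a quantitative claim about log10 RNA, and the plan analyses a yes/no cut. A difference in the proportion below 20 copies/mL is a different estimand from a difference in log10 RNA, so testing one does not test the other. The same line of Section 12 writes CD4 as a change and viral load as a threshold, which makes it hard to read the threshold as shorthand for a change.

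The wording also leaves the sign open. Eligibility covers people already prescribed ART and people only eligible for it, with no viral-load entry threshold. Someone already suppressed can hardly change, while someone starting ART may fall by several logs. If change is read as amount of movement rather than as a signed difference, the two readings can rank the arms in opposite order.

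With suppression named in the aim and log10 change named in the hypotheses, the choice of viral-load endpoint could also be made after the data are seen.

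**Working it through.** The plan states no effect size, SD, suppression rate, alpha or power for viral load, so there is no planned figure to reproduce. The check is a matching exercise followed by an illustration of what the binary cut gives up.

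**1. Match each element to an analysis.**

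| Element of hypotheses 2 and 5 | Where it appears in Section 12 |
|---|---|
| Change in log10 HIV-1 RNA | Nowhere; viral load enters only as VL<20 or as suppression |
| CD4 count | Change in CD4, outcome group (c) |
| Retention in care | Not in outcome groups (a) to (d), but named as an outcome in the mediation and moderation step |

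One element of three is unmatched.

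**2. Sign.** Take two example changes, follow-up minus baseline: −2.0 and −0.5 log10.
- Signed reading: −2.0 < −0.5, so the lower change is the larger fall, which is improvement.
- Magnitude reading: 0.5 < 2.0, so the lower change is the smaller fall, which is less improvement.

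The sentence frames the element as an improved outcome, which favours the signed reading, but no section defines it.

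**3. Assay floor.** With a floor of 20, the cut at 20 coincides with the limit of quantification. With a floor of 50, results below 50 cannot be sorted into below 20 and 20 to 50, so VL<20 cannot be determined. A left-censored log10 model can use either limit once it is stated.

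**4. Information kept by VL<20.** Assumptions: latent log10 RNA is normal, the arms differ by a small shift in mean, the floor equals the cut, and baseline adjustment is ignored in both analyses. Let p be the proportion suppressed, z = Φ⁻¹(p) and φ the normal density at z. Information per participant about the mean, in units of 1/σ², is:
- binary: φ² / [p(1−p)]
- left-censored (Tobit): (1−p) + zφ + φ²/p

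| p | z | φ | Binary | Tobit | Binary ÷ Tobit |
|---|---|---|---|---|---|
| 0.3 | −0.524 | 0.348 | 0.576 | 0.700 − 0.182 + 0.403 = 0.921 | 63% |
| 0.5 | 0 | 0.399 | 0.637 | 0.500 + 0 + 0.318 = 0.818 | 78% |
| 0.8 | 0.842 | 0.280 | 0.490 | 0.200 + 0.236 + 0.098 = 0.534 | 92% |
| 0.9 | 1.282 | 0.175 | 0.342 | 0.100 + 0.225 + 0.034 = 0.359 | 95% |

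The Binary column is also the fraction kept relative to a fully observed normal outcome (64%, 49% and 34% at p = 0.5, 0.8 and 0.9). That comparison does not apply when the cut is the assay floor, because values below it are not observed under any analysis. The relevant comparison is the last column, where the loss shrinks as suppression rises.

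**The case against.** The strongest reply is that viral suppression is the declared secondary outcome in Aim 2 and again in the mediation step. On that view the analysis matches the declared outcome and only the hypothesis wording is loose. This is a secondary outcome in a pilot that makes no power claim, and the halting rules say no efficacy difference is expected. All of that stands, and it limits how much weight the point can bear. It does not remove the mismatch, since the hypothesis and the analysis still name different quantities.

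Four stronger readings are tempting, and the documents do not support them:

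- **That the hypothesised direction is wrong.** The phrase sits under improved outcomes, and on a signed scale a lower change is a larger fall. It is ambiguous, not reversed.
- **That two of the seven hypotheses go untested.** Change in CD4 is a listed outcome and retention is named in the mediation and moderation step. Only the RNA element lacks an analysis.
- **That baseline viral load is ignored.** Section 12 enters pre-intervention scores as covariates for the main outcomes. It does not say in what form baseline viral load would enter, but neither does it exclude it.
- **That the cut discards most of the information.** Against the left-censored alternative it keeps well over half at every split shown above.

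**Conclusion.** The point holds for the RNA element alone: it has no sign convention and no planned analysis. The precision cost of relying on VL<20 is modest, about 22% of the censored model's information at 50% suppressed, 8% at 80% and 5% at 90%. Those figures rest on the latent-normal assumption, a floor equal to the cut, and suppression rates that the documents do not give. At an assumed 30% suppressed the loss would be about 37%.

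The better reason to change the plan is that the data for the stated hypothesis will already exist and one added model would test it. The conflicting assay limits bear on the same endpoint and must be settled first, because with a floor of 50 even the declared VL<20 outcome could not be scored. For a secondary outcome in a pilot this is a cheap and worthwhile correction, not a threat to the trial's main conclusions.

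**What to change.** 1. **Reconcile the assay lower limit** between Research Plan 2.E, item 3 (50 copies/mL) and Section VIII, Data Sources, item 4 (20 copies/mL). If samples were run under both limits, record the limit that applied to each result.
2. **Reword the RNA element** of hypotheses 2 and 5 as: *lower week-12 log10 HIV-1 RNA, adjusted for baseline*. This removes the sign problem. Week 12 is the post-baseline time that both measurement sections share.
3. **Add to Section 12, Aim 2** a secondary analysis of week-12 log10 RNA with baseline log10 RNA as covariate, treating results below the assay floor as left-censored. State how a baseline value below the floor is coded.
4. **Keep VL<20** as the declared binary secondary outcome.

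The cost is one reworded sentence and one model on data already being collected. The downside is one more secondary analysis, which will carry limited information if most participants are suppressed and which, with arms of 20, 20, 20 and 30, leans on the normality assumption.

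If the sponsor wants suppression only, restating the RNA element as the proportion with VL<20 also closes the mismatch without a new model, but it gives up the quantitative claim and still requires step 1.
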